## 5.3 Restrictions on Concomitant Therapies

### 5.3.1 Non-Permitted Concomitant Therapies

Subject **may not** receive the following concomitant therapies during the study:

1.	Systemic treatment with corticosteroids (greater than Prednisone 10 mg daily or equivalent) or other immunosuppressive treatments (e.g., methotrexate, chloroquine, azathioprine). See Section 5.3.2 for exceptions. [Wash-out period: 2 weeks prior to Day 1.]
2.	Other cancer therapy (e.g., drug, non-palliative radiation, or immunotherapy). [Wash-out period: 4 weeks or 5 half-lives (whichever is shorter) prior to Day 1 (6 weeks for nitrosoureas)].
3.	Live/attenuated vaccines 1 month prior to Day 1 and for at least 6 months after the last dose of treatment.
4.	Sunitinib within 3 months after the last dose of tremelimumab.
5.	Drugs with laxative properties and herbal or natural remedies for constipation should generally be avoided through 90 days post last dose of tremelimumab because of the potential for exacerbation of diarrhea, but, for example, opiate-induced constipation may be treated with laxatives at the Investigator's discretion.
6.	

• Systemic immunosuppressive drugs including systemic steroid doses of <math>\geq 10</math> mg prednisone equivalent per day are prohibited. In case immunosuppressive therapy, or treatment with steroids <math>\geq 10</math> mg prednisone equivalent per day <math>>3</math> days, is clinically mandated due to an intercurrent illness, it should be agreed upon with the Sponsor whether continuation of BI 1361849 can be allowed, and the possible risks to continue the vaccine treatment during the intercurrent illness should be judiciously weighed against the potential benefit of continued treatment.

• Any treatments that have immunostimulatory properties including mistletoe extract are prohibited and should be discontinued at least 2 weeks prior to Day 1.

• No local anesthetics for the vaccination procedure are allowed.

The wash-out period prior to Day 1 of the study for all non-permitted drugs should be at least 1 week, unless stated otherwise above.	

CONFIDENTIAL

### 5.3.2 Permitted Concomitant Therapies

Subject **may** receive the following concomitant therapies during the study:

1.	Inhaled or oral steroids for treating mild to moderate asthma or allergies, or topical steroids for localized (< 5% of body surface area) dermatitis, not to exceed 10 mg/day prednisone or bioequivalent corticosteroid.
2.	Physiologic replacement of glucocorticoids as maintenance therapy for adrenal insufficiency. Standard doses of hydrocortisone for maintenance therapy are up to 10–20 mg/m  /day divided 2–4 times per day. For a subject with a body surface area (BSA) of 1.73 m  , this translates to a total dose of up to 34.6 mg of hydrocortisone per day. The equivalent dose of dexamethasone is up to 1.2 mg per day. Some subjects may additionally receive mineralocorticoid-replacement maintenance therapy with fludrocortisone. The maintenance dose of fludrocortisone for this indication is 0.05–0.1 mg/day.
3.	NSAIDs, acetylsalicylic acid, and specific COX-2 inhibitors.
4.	Antihistamines and other non-steroidal anti-allergy medication.
5.	Hormone or hormone-related anti-cancer therapy.
6.	At the discretion of the Investigator, any drug or non-drug therapy necessary to treat any condition arising during the study, including high-dose corticosteroids to treat immune-mediated adverse reactions. Subjects should receive full supportive care, including transfusions of blood and blood products, and treatment with antibiotics, anti-emetics, anti-diarrheal, and analgesics, and other care as deemed appropriate, and in accordance with their institutional guidelines. Use of anticoagulants such as warfarin is permitted; however, caution should be exercised and additional international normalized ratio (INR) monitoring is recommended.
All prescription and nonprescription drugs and herbal supplements must be recorded in the concomitant medications section of the case report form, listing generic (preferably) or brand name, indication, dose, route, and dates of administration. All non-drug therapies must be recorded in the respective sections of the case report form.	

CONFIDENTIAL

## 6 Study Drug Preparation and Administration

All study drugs are supplied by the Sponsor (see Section 7.2.8). Commercially available 0.9% (w/v) saline or 5% (w/v) dextrose will be supplied by each site. BI 1361849 requires reconstitution with Ringer's lactate solution (see Section 6.3.2).

On the days when both tremelimumab and durvalumab are to be administered, the durvalumab infusion will start at least 60 minutes after the end of the tremelimumab infusion. The BI 1361849 injections will start at least 60 minutes after the end of the durvalumab infusion is completed when injections and infusions occur on the same day.

See Section 6.5 for monitoring of subjects during tremelimumab, durvalumab and BI 1361849 dose administrations.

### 6.1 Durvalumab (MEDI 4736)

#### 6.1.1 Study Drug Information

Manufacturer	MedImmune		
Expiration/Retest Date	Expiration/retest dates are documented in the QA Disposition of Investigational Medicinal Product (IMP) Report.		
Container Description	Type: Single use vial	Material: clear glass	Size: 10 mL
Formulation	Liquid solution containing 500 mg durvalumab per vial. The solution contains 50 mg/mL durvalumab, 26 mM histidine/histidine-HCl, 275 mM trehalose dihydrate, 0.02% (weight/volume [w/v]) polysorbate 80, at pH 6.0.		
Active Ingredient Content	Mass/Weight: 500 mg	Volume: 10mL	Concentration: 50 mg/mL
Storage Conditions	2°C to 8°C (36°F to 46°F) Do not freeze		
Labeling	Product name, lot number, and storage conditions		

#### 6.1.2 Durvalumab Investigational Product Inspection

Each vial of durvalumab selected for dose preparation should be inspected. If there are any defects noted with the investigational product (IP), the Investigator and Sponsor should be notified immediately. See Section 7.2.8 for additional details.

#### 6.1.3 Durvalumab Preparation

The dose of durvalumab for administration must be prepared by the IP manager or designated personnel using aseptic technique. No incompatibilities between durvalumab and polyvinylchloride or polyolefin copolymers have been observed.

CONFIDENTIAL

Dose Calculation:

Subjects will receive a fixed dose of durvalumab:

- **Starting dose:1500 mg Q4W**

NOTE: the durvalumab dose of 1500 mg Q4W is for subjects > 30 kg. If a subject's body weight drops to ≤ 30 kg while on the study, the subject will receive weight-based dosing equivalent to 20 mg/kg of durvalumab as long as the body weight remains ≤ 30 kg (e.g., a 30 kg subject would receive a 600 mg dose; a 25 kg subject would receive a 500 mg dose; etc.). When the weight improves to >30 kg, the subject may return to fixed dosing of durvalumab 1500 mg.

- **Dose de-escalation: 750 mg Q4W**

The volume of durvalumab (in mL) to be added to the IV bag is calculated as follows:

Volume of Durvalumab (mL)	=	Dose level (mg)	÷	Durvalumab Concentration (nominal 50 mg/mL)
---------------------------	---	-----------------	---	---

Dose Preparation:

Durvalumab will be administered using an IV bag containing 0.9% (w/v) saline or 5% (w/v) dextrose and delivered through an IV administration set with a 0.2 or 0.22 µm in-line filter. The final durvalumab concentration after dilution in the bag must be 1 mg/mL to 15 mg/mL. The calculated volume of durvalumab is added to the IV bag, and the bag is mixed by gentle inversion to ensure homogeneity of the dose in the bag.

*Example:* For a 1500 mg dose (for subjects > 30 kg in weight), 30 mL of durvalumab may be diluted in a 250 mL IV bag, and the bag is mixed by gentle inversion.

Durvalumab does not contain preservatives; any unused portion must be discarded.

### 6.1.4 Durvalumab Administration

Following preparation of the dose, durvalumab will be administered according to the following guidelines:

- A physician must be present at the site or immediately available to respond to emergencies during all administrations of investigational products. Fully functional resuscitation facilities should be available.
- Prior to the start of the infusion, the IV bag contents must be at room temperature to avoid an infusion reaction due to the administration of the solution at low temperatures.
- Durvalumab must not be administered via IV push or bolus, but as an IV infusion.
- Durvalumab solution should not be infused with other solutions or medications.
- Durvalumab must be administered at room temperature by controlled infusion into a peripheral vein or central line.
- The entire contents of the IV bag should be administered as an IV infusion over approximately 60 (± 5) minutes (a 0.2- or 0.22-µm in-line filter is required). **An infusion of less than 55 minutes is considered a deviation.**

- After the contents of the IV bag are fully administered, the IV line will be flushed with a volume of IV diluent equal to the priming volume of the infusion set used. Alternatively, the infusion will be completed according to institutional policy to ensure the full dose is administered; documentation is required if the line was not flushed.
- The total time between needle puncture of the durvalumab vial to start of administration should not exceed 4 hours at room temperature or 24 hours at 2°C to 8°C (36°F to 46°F). Standard infusion time is 60 ± 5 minutes (an infusion of less than 55 minutes is considered a deviation). However, if there are interruptions during infusion, the total allowed infusion time should not exceed 8 hours. In the event that either preparation time or infusion time exceeds the time limits, a new dose must be prepared from new vials.
- The date, start time, interruption, and completion time of durvalumab administration must be recorded in the source documents.
- Subjects will be monitored before, during and after infusion with assessment of vital signs according to Section 6.5.
- See Section 8.3.1 for guidelines for infusion-related reactions.

---

CONFIDENTIAL

## 6.2 Tremelimumab

### 6.2.1 Study Drug Information

Manufacturer	MedImmune		
Expiration/Retest Date	Expiration/retest dates are documented in the QA Disposition of IMP Report.		
Container Description	Type: Single use vial	Material: Clear glass	Size: 20 mL
Formulation	Liquid solution containing 400 mg tremelimumab per vial. The solution contains 20 mg/mL tremelimumab, 20 mM histidine/histidine hydrochloride, 222 mM trehalose dihydrate, 0.27 mM disodium edetate dihydrate, and 0.02% weight/volume (w/v) polysorbate 80; it has a pH of 5.5.		
Active Ingredient Content	Mass/Weight: 400 mg	Volume: 20 mL	Concentration: 20 mg/mL
Storage Conditions	2°C to 8°C (36°F to 46°F) Do not freeze		
Labeling	Product name, lot number, and storage conditions		

Tremelimumab is also available in a 25 mg/vial format; the concentration remains 20 mg/mL.

Manufacturer	MedImmune		
Expiration/Retest Date	Expiration/retest dates are documented on the QA Disposition of Investigational Medicinal Product (IMP) Report.		
Container Description	Type: Single-use vial	Material: Clear glass	Size: 2 mL
Formulation	Liquid solution containing 25 mg tremelimumab per vial. The solution contains 20 mg/mL tremelimumab, 20 mM histidine/histidine hydrochloride, 222 mM trehalose dihydrate, 0.27 mM disodium edetate dihydrate, and 0.02% weight/volume (w/v) polysorbate 80; it has a pH of 5.5.		
Active Ingredient Content	Mass/Weight: 25 mg/vial	Volume: 1.25 mL/vial	Concentration: 20 mg/mL
Storage Conditions	+2°C to +8°C (36°F to 46°F). Do not freeze.		
Labeling	Product name, lot number, and storage conditions		

### 6.2.2 Tremelimumab Investigational Product Inspection

Each vial of tremelimumab selected for dose preparation should be inspected. If there are any defects noted with the investigational product (IP), the Investigator and Sponsor should be notified immediately. See Section 7.2.8 for additional details.

### 6.2.3 Tremelimumab Preparation

The dose of tremelimumab for administration must be prepared by the IP manager or designated personnel using aseptic technique. No incompatibilities between tremelimumab and polyvinylchloride or polyolefin have been observed.

CONFIDENTIAL

Dose Calculation:

Subjects will receive a fixed dose of tremelimumab: 75 mg Q4W (x4). When tremelimumab is given with durvalumab 1500 mg Q4W, if a subject’s body weight drops to ≤ 30 kg while on the study, the subject will receive weight-based dosing for both drugs. For durvalumab, the weight-based dosing is described in Section 6.1.3; for tremelimumab, weight-based dosing equivalent to 1 mg/kg tremelimumab will be given as long as the body weight remains ≤ 30 kg (e.g., a 30 kg subject would receive a 30 mg dose; a 25 kg subject would receive a 25 mg dose; etc.). When the weight improves to >30 kg, the subject may return to fixed dosing of tremelimumab 75 mg and durvalumab 1500 mg.

The volume of tremelimumab (in mL) to be added to the IV bag is calculated as follows:

Tremelimumab Dose (mL)	=	dose level (mg)	÷	Tremelimumab concentration (20 mg/mL)
---------------------------	---	-----------------	---	---

Dose Preparation:

Tremelimumab will be administered using an IV bag containing 0.9% (w/v) saline or 5% (w/v) dextrose and delivered through an IV administration set with a 0.2- or 0.22-µm in-line filter. The final concentration of tremelimumab after dilution in the bag must be between 0.10 mg/mL and 10 mg/mL. The calculated volume of tremelimumab is added to the IV bag, and the bag is mixed by gentle inversion to ensure homogeneity of the dose in the bag.

*Example:* The volume of tremelimumab required for 75 mg dose is 3.75 mL and may be administered using a 250 ml bag.

The corresponding volume of investigational product should be rounded according to institutional practice. For example, (for a 75 mg dose of tremelimumab), if the institutional practice is to round the volume to the nearest tenth mL, 3.75 mL would be rounded to 3.8 mL, which would be the volume of tremelimumab added to the bag; the bag is then mixed by gentle inversion.

Tremelimumab does not contain preservatives; any unused portion must be discarded.

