### 3.1.7 Treatment Arms and Treatment Schema

Study drug will be administered over 12 cycles with a cycle length of 28 days. The study drugs used in this study will be administered per cycle as shown below:

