**Note: the dosing intervals for BI 1361849 intervals increase over time**

Cycle (28d)	Cycle Day	Arm A Dosing Schedule		Arm B Dosing Schedule		
		BI 1361849 (12 x i.d. each)	Durvalumab (i.v.)	BI 1361849 (12 x i.d. each)	Durvalumab (i.v.)	Tremelimumab* (i.v.)
1	1	X	X	X	X	X
	8	X		X		
	15	X		X		
2	1	X	X	X	X	X
	15	X		X		
3	1	X	X	X	X	X
	15	X		X		
4	1	X	X	X	X	X
5	1	X	X	X	X	
6	1	X	X	X	X	
7	1		X		X	
	15	X		X		
8	1		X		X	
9	1	X	X	X	X	
10	1		X		X	
	15	X		X		
11	1		X		X	
12	1	X	X	X	X	X

i.d. = intradermal; i.v. = intravenous

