**NOTE 2:**

- **The durvalumab dose of 1500 mg Q4W is for subjects > 30 kg.** If a subject's body weight drops to ≤ 30 kg while on the study, the subject will receive weight-based dosing equivalent to 20 mg/kg of durvalumab as long as the body weight remains ≤ 30 kg (e.g., a 30 kg subject would receive a 600 mg dose; a 25 kg subject would receive a 500 mg dose; etc.). When the weight improves to >30 kg, the subject may return to fixed dosing of durvalumab 1500 mg.
- **When tremelimumab 75 mg Q4W (x4) is given with durvalumab 1500 mg Q4W,** if a subject's body weight drops to ≤ 30 kg while on the study, the subject will receive weight-based dosing for both drugs. For durvalumab, the weight-based dosing is described above; for tremelimumab, weight-based dosing equivalent to 1 mg/kg tremelimumab will be given as long as the body weight remains ≤ 30 kg (e.g., a 30 kg subject would receive a 30 mg dose; a 25 kg subject would receive a 25 mg dose; etc.). When the weight improves to >30 kg, the subject may return to fixed dosing of tremelimumab 75 mg and durvalumab 1500 mg.

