### 3.1.9 DLT and MTD/RCD for the Combination Therapy

MTDs will not be determined in this study. Instead, RCDs will be determined in the context of the predefined dose levels used during the dose evaluation phase as per Section 3.1.7.1.

DLTs will be observed over a period of the first 2 cycles of the combination therapy, including the pre-dose assessment for Cycle 3, defined as the **DLT Evaluation Period**. The decisions for dose evaluations, de-escalations and RCD, as described in Section 3.1.7.1 will primarily be based on the number of subjects with DLTs occurring during the DLT Evaluation Period. DLTs occurring outside the DLT Evaluation Period will also be evaluated and may impact such decisions.

DLTs are defined as any adverse events that are possibly, probably, or definitely related to the administration of durvalumab, tremelimumab, or BI 1361849 components, and fulfill any of the following criteria:

1. Any Grade  $\geq 3$  colitis, pneumonitis, neurological event or uveitis.
2. Any Grade 2 pneumonitis, neurological event or uveitis, with the following exception:
  - Grade 2 pneumonitis, neurological event or uveitis that downgrade to Grade  $\leq 1$  within 3 days after onset, whereby maximal supportive care, including systemic corticosteroids, is permitted.
3. Any *other* Grade  $\geq 3$  toxicity, with the following exceptions:
  - Grade 3 irAEs that downgrade to Grade  $\leq 2$  within 3 days, or to Grade  $\leq 1$  or baseline within 14 days after onset, whereby maximal supportive care, including systemic corticosteroids, is permitted.
  - Grade 3 endocrinopathy that becomes asymptomatic when managed with or without systemic corticosteroid therapy and/or hormone replacement therapy.
  - Grade 3 inflammatory reaction attributed to a local antitumor response (e.g., inflammatory reaction at sites of metastatic disease, lymph nodes, etc.).
  - Grade 3 fatigue for  $\leq 7$  days.
  - Grade 3 infusion-related reaction (first occurrence and in the absence of steroid prophylaxis) that resolves within 6 hours with appropriate clinical management.
  - Liver transaminase elevation  $\leq 8$  times ULN that downgrades to Grade  $\leq 2$  ( $\leq 5$  times ULN) within 7 days after onset, whereby maximal supportive care, including systemic corticosteroids, is permitted.

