### 3.2 Study Flowchart

LUD2014-012-VAC Study Flowchart	Screening / Baseline	Treatment (each cycle = 4 weeks)											
		Cycle 1			Cycle 2			Cycle 3		Cycle 4		Cycle 5	Cycle 6
Study Week		1	2	3	5	6 J	7	9	11	13	14 J	17	21
Cycle Day		1	8 (±2)	15 (±2)	1 (±2)	8 (±2)	15 (±2)	1 (±2)	15 (±2)	1 (±2)	8 (±2)	1 (±3)	1 (±3)
Cumulative Study Day	Up to 1 month before Tx start	1	8	15	29	36	43	57	71	85	92	113	141
Treatment													
Durvalumab (Arms A and B)		X			X			X		X		X	X
Tremelimumab (Arm B)		X			X			X		X			
BI 1361849 - 6 components (Arms A and B)		X	X	X	X		X	X	X	X		X	X
Tumor and Disease Assessments													
Disease Staging (date/stage at 1st diagnosis and at study entry)	X												
Disease Assessment by irRECIST/RECIST a	X							X				X	
Study Procedures and Examinations													
Eligibility Assessment and Informed Consent (IC) h	X												
Demographics (incl. DoB; sex; height; race; ethnicity)	X												
Medical history	X												
Physical Exam (incl. weight and ECOG Perf Status) b	X	X	X	X	X		X	X	X	X		X	X
12-Lead ECG a	X	X			X					X			X
Vital Signs (T, HR, BP, RR) e	X	X	X	X	X		X	X	X	X		X	X
Concomitant Medication(s)/ Procedure(s)	X	X	X	X	X	X	X	X	X	X	X	X	X
Adverse Events (starting or worsening after IC) f	X	X	X	X	X	X	X	X	X	X	X	X	X
Specimens for Routine Laboratory Procedures													
Blood Hematology (complete blood count, differential, platelets) a	X	X	X	X	X	X	X	X	X	X	X	X	X
Chemistry (glucose, BUN, creat., Na, K, Cl, CO 2 , Ca, Mg, protein, albumin, Tbili., AST, ALT, ALP, LDH) a	X	X	X	X	X		X	X	X	X		X	X
Chemistry cont. (Free T 3 , Free T 4 , TSH) a	X	X	X	X	X		X	X	X	X		X	X
Chemistry cont. (Amylase and lipase) a	X	X	X	X	X		X	X	X	X		X	X
Urinalysis a,c	X	X			X			X		X		X	X
Coagulation parameters a,d	X												
Serum pregnancy test (Urine test only on Day 1) a	Up to 1 week before Tx start	X						X				X	
Specimens for Other Peripheral Blood AssaysL													
Blood for exosomal profiling a		X			X								
Blood for PaxGene RNA and DNA a,k Note: Discontinued per Amendment 9.1		X				X J					X J		
Blood (PBMC and plasma) for flow cytometry and biological assays a,i,k Note: Discontinued per Amendment 9.1		X				X J					X J		

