## 8.0 TRIAL DRUG EXPOSURE AND COMPLIANCE

Extent of treatment exposure to durvalumab, will be assessed for each of the two study arms. Durvalumab exposure (Arms A and B) will be summarized by the following parameters:

- Duration of durvalumab treatment (week), calculated as:  $(\text{Last dose date} - \text{first dose date} + 1) / 7$
- Number of durvalumab doses
- Total durvalumab dose (mg), defined as the sum of the actual doses (mg) administered
- Number of subjects with durvalumab dose de-escalated (only in Arm A)

Tremelimumab exposure (Arm B) will be summarized by the following parameters:

- Duration of Tremelimumab treatment (week), calculated as:  $(\text{Last dose date} - \text{first dose date} + 1) / 7$
- Number of tremelimumab doses
- Total Tremelimumab dose (mg), defined as the sum of the actual doses (mg) administered

BI 1361849 exposure (Arms A and B) will be summarized by the following parameters:

- Duration of BI 1361849 treatment (week), calculated as:  $(\text{Last dose date} - \text{first dose date} + 1) / 7$
- Number of doses
- Total BI 1361849 dose ( $\mu\text{g}$ ), defined as the sum of the actual doses (mg) administered

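### The Protocol 3.1.7 dosing table schedules five tremelimumab doses in Arm B; every other schedule in the Protocol and SAP gives four

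*Protocol*

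**What the plan says.** Protocol Section 3.1.7 introduces its dosing table with "The study drugs used in this study will be administered per cycle as shown below". The table has five drug columns: vaccine and durvalumab for Arm A, then vaccine, durvalumab and tremelimumab for Arm B. In the tremelimumab column it marks Day 1 of Cycles 1 to 4, nothing in Cycles 5 to 11, and Day 1 of Cycle 12. The one note printed with the table concerns the vaccine only ("the dosing intervals for BI 1361849 intervals increase over time"). The tremelimumab column heading carries an asterisk, for which the available text shows no footnote.

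Elsewhere the count is four:

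- Protocol 6.2.3: "Subjects will receive a fixed dose of tremelimumab: 75 mg Q4W (x4".
- Protocol 3.1.7.1, Note 2: "When tremelimumab 75 mg Q4W (x4) is given with durvalumab 1500 mg Q4W".
- Protocol 3.2 flowchart, Cycles 1 to 6: "Tremelimumab (Arm B) X X X X", at study weeks 1, 5, 9 and 13. The tremelimumab row on the Cycle 7 to 12 page is empty.
- SAP Appendix A repeats that flowchart.
- SAP Appendix B has the same layout as the Protocol 3.1.7 table, but its Cycle 12 tremelimumab cell is empty.

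**The concern.** The Protocol tells sites to give the drugs as the 3.1.7 table shows, and elsewhere states a different number of tremelimumab doses. It does not say which place takes precedence. A site working from the dosing table and a site working from the flowchart or the pharmacy section could treat an Arm B subject differently at Cycle 12, and each would be deviating from another part of the same Protocol.

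Three things are at stake: subject safety, because the question is whether an investigational antibody is given on a particular day; the definition of the regimen to which the Arm B safety and efficacy results refer; and the exposure tables and post-treatment restrictions that depend on the date of the last tremelimumab dose.

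**Working it through.** **Inputs.** The dose is 75 mg (Protocol 6.2.3). Study days come from the Section 3.2 flowchart: Cycles 1, 2, 3, 4 and 12, Day 1, are days 1, 29, 57, 85 and 309. The SAP Section 8.0 item "Duration of Tremelimumab treatment (week), calculated as" uses (last dose date − first dose date + 1)/7. The calculation assumes a subject above 30 kg throughout, no missed doses, and visits on their nominal days.

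**Step 1: count the scheduled doses.**

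| Source | Tremelimumab given at | Doses |
|---|---|---|
| Protocol 6.2.3 | Q4W, four times | 4 |
| Protocol 3.1.7.1 Note 2 | Q4W, four times | 4 |
| Protocol 3.2 flowchart | Cycles 1–4 | 4 |
| SAP Appendix A | Cycles 1–4 | 4 |
| SAP Appendix B | Cycles 1–4 | 4 |
| Protocol 3.1.7 table | Cycles 1–4 and 12 | 5 |

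The stated count of four is reproduced by the flowchart and both SAP appendices, but not by the 3.1.7 table.

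**Step 2: cumulative dose.** 4 × 75 = 300 mg; 5 × 75 = 375 mg. The difference is 75 mg, and 75/300 = 25%.

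**Step 3: dosing intervals.** Cycles 1 to 4: 29 − 1 = 57 − 29 = 85 − 57 = 28 days. Cycle 4 to Cycle 12: 309 − 85 = 224 days = 32 weeks. The fifth mark therefore does not fit a four-weekly interval.

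**Step 4: SAP exposure duration.** Four doses: (85 − 1 + 1)/7 = 12.14 weeks. Five doses: (309 − 1 + 1)/7 = 44.14 weeks. The number of doses and the total dose change as well.

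**Step 5: restrictions timed from the last dose.** Contraception and blood-donation limits run to the later of 90 days after durvalumab or 6 months after tremelimumab (Protocol 5.2). Take a subject dosed with durvalumab through day 309, and 6 months as 183 days (an assumption).

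- Four doses: tremelimumab limit 85 + 183 = day 268; durvalumab limit 309 + 90 = day 399. Durvalumab governs, at day 399.
- Five doses: tremelimumab limit 309 + 183 = day 492. Tremelimumab governs, at day 492.
- Difference: 492 − 399 = 93 days, about three months.

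The sunitinib and laxative restrictions in Protocol 5.3.1 also run from the last tremelimumab dose, so their end dates move by 224 days.

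**Step 6: can the supply estimate decide it?** Protocol 6.4 lists 128 tremelimumab vials of 400 mg. At one vial per dose (an assumption), that covers 128/4 = 32 subjects or 128/5 = 25.6 subjects. Both exceed the 20 planned for Arm B, so the estimate does not discriminate.

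**Not affected.** The DLT period and both per-protocol dose criteria cover the first two cycles. The sample-size reasoning does not use the tremelimumab schedule.

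**The case against.** The strongest counter-argument is that the finding rests on one table cell in text read from a PDF. The SAP copy of the table, based on Amendment 9.1, leaves that cell empty, and a misread mark cannot be excluded without the printed page. That caution stands, and the page should be checked. It is not enough to set the point aside. A displaced mark would leave a gap elsewhere in the row, but the Cycle 12 row has five marks for five columns, while the Cycle 9 row of the same table has four marks and an empty tremelimumab cell. The conflict lies in current body text, not in the amendment history.

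A second argument is that sites would not give a fifth dose, because both the visit flowchart and the pharmacy section point to four. That makes different treatment a risk rather than a certainty, and confines it to Arm B subjects still on treatment at day 309. The documents do not allow that number to be estimated. But Section 3.1.7 directs administration by its own table, and nothing ranks the other places above it.

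A third is that the consequences adjust themselves: SAP 8.0 sums the doses actually given, and the restrictions run from each subject's actual last dose. This is correct as bookkeeping. It means a fifth dose would appear in the tables; it does not establish whether that dose was intended or a deviation.

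Finally, the orphan asterisk appears in both the Protocol and SAP copies of the table, so it is not evidence for a Cycle 12 dose. Its footnote may have been lost in extraction. It is a loose end only.

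**Conclusion.** The concern holds. The Protocol contradicts itself, and its 3.1.7 table contradicts the SAP, on whether tremelimumab is given at Cycle 12 Day 1. The size is one dose of 75 mg: 375 mg against 300 mg in total, with SAP exposure duration of 44.14 against 12.14 weeks, for each Arm B subject who reaches Cycle 12 on full dosing at the nominal days. The conclusion assumes that the printed 3.1.7 table shows the mark that the extracted text shows. Because it concerns administration of a study drug and the regimen that Arm B represents, it must be corrected. The documents agree on four everywhere except the table that governs administration; which schedule is right is for the sponsor to determine.

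**What to change.** 1. Check the printed Cycle 12 row of the Protocol 3.1.7 table.
2. Have the sponsor determine the intended tremelimumab schedule and reconcile Protocol 3.1.7, 3.1.7.1, 3.2 and 6.2.3 and SAP Appendices A and B so that all show it.
3. Supply the footnote for the asterisk on the tremelimumab column, or remove the asterisk, in both the Protocol and SAP copies of the table.
4. Notify sites of the reconciled schedule.
5. In the exposure listing, identify each Arm B subject who reached Cycle 12 and whether tremelimumab was given there, so that any departure from the reconciled schedule is visible when exposure and safety are reported.

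The cost is an administrative Protocol correction with a site notice, a matching SAP check and one flag in a listing. No analysis method or sample size changes.
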